CSR	Clinical Study Report
DED	Dry Eye Disease
DFE	Dilated Fundus Exam
eCRF	Electronic Case Report Form
ENR	Enrolled Population
EOS	End of Study
EOT	End of Treatment
ET	Early Termination
EU	European Union
FAS	Full Analysis Set
FCS	Fully Conditional Specification
FTBUT	Fluorescein Tear Break-Up Time
IB	Investigator Brochure
ICE	Intercurrent Event
ICF	Informed Consent Form
IMP	Investigational Medicinal Product
IRT	Interactive Response Technology
LogMAR	Logarithm of the Minimum Angle of Resolution (Chart)
LS	Least Square
MAR	Missing at Random
MedDRA	Medical Dictionary for Regulatory Activities
mcg/mL	micrograms/milliliter
mcL	microliter

MI	Multiple Imputation
MMRM	Mixed Model for Repeated Measures
MNAR	Missing Not at Random
CC	
CCI	
NIMP	Non Investigational Medicinal Product
CCI	
PD	Protocol Deviation
PP	Per Protocol Population
PT	Preferred Term
QoL	Quality of Life
Q1	first quartile (lower quartile)
Q3	third quartile (upper quartile)
RCT	Randomized Clinical Trial
rhNGF	recombinant human Nerve Growth Factor
RND	Randomized Population
SAE	Serious Adverse Event
SAF	Safety Population
SANDE	Symptom Assessment in Dry Eye
SAP	Statistical Analysis Plan
SCR	Screened Population
SD	Standard Deviation
SE	Standard Error
SLE	Slit-Lamp Examination
SOC	System Organ Class
TEAE	Treatment Emergent Adverse Event
CC	
USA	United States of America
V	Visit
CCI	
VBR	Validated Bulbar Redness scale
Vs	Versus
WHODrug	World Health Organization Drug Dictionary

Revision History

Version	Changes Made	Document Date
Final 1.0	First release.	CCI [REDACTED]
Final 2.0	CCI [REDACTED] [REDACTED] [REDACTED] [REDACTED] [REDACTED] [REDACTED] [REDACTED] [REDACTED] [REDACTED] [REDACTED] [REDACTED] [REDACTED] [REDACTED] [REDACTED] [REDACTED]	25Feb2025

1. Introduction

This statistical analysis plan (SAP) describes the analyses and data presentations for Dompé's protocol REDUCO "A 4-Week, Phase II, Multicenter, Randomized, Double-Masked, Vehicle-Controlled, Parallel Group Study With 4 Weeks of Follow-Up to Evaluate Safety and Efficacy of a new formulation of Recombinant Human Nerve Growth Factor (rhNGF) CCI Solution at two different Concentrations in patients with Dry Eye Disease" which was issued on 16Nov2023. This SAP is aligned with version 3.0 of the protocol, dated 11Mar2024. It contains definitions of analysis populations, derived variables, and statistical methods for the analyses of efficacy and safety.

The study plans only a final analysis: this analysis will be conducted when all randomized patients have completed the study (completed treatment at week 4 (visit 4) and completed follow-up at week 8 (visit 5)) and the study database has been locked and all personnel have been unmasked.

The purpose of the SAP is to ensure the credibility of the study findings by pre-specifying the statistical approaches to the analysis of study data prior to database lock and final analyses. This SAP will be finalized and signed prior to the clinical database lock for the final analyses. Additional post-hoc analysis may be produced to allow further comparisons between treatment and control, according to the results obtained.

This SAP is to be interpreted in conjunction with the protocol. Should the SAP and protocol be inconsistent with respect to the planned analyses, the language of the SAP is governing. If the final clinical study report (CSR) contains changes to any planned statistical analyses (including unplanned analyses), the justification for any such differences will be fully documented in the CSR.

2. Objectives

2.1. Primary Objective

- To evaluate the efficacy of C mcg/mL and C mcg/mL concentrations of the new formulation of rhNGF ophthalmic solution versus vehicle, in order to demonstrate superiority of at least one of the concentrations over vehicle in the improvement of ocular symptoms of dry eye in patients with dry eye disease (DED) at Week 8.

2.2. Key Secondary Objectives

- To evaluate the efficacy of the new formulation of rhNGF ophthalmic solution in increasing the number of patients with improved reflex tear production as compared to vehicle at week 4.
- To evaluate the efficacy of the new formulation of rhNGF ophthalmic solution in improving reflex tear production as compared to vehicle at week 4.
- To evaluate the efficacy of the new formulation of rhNGF ophthalmic solution in improving ocular surface integrity (corneal epitheliopathy) as compared to vehicle at week 4.

2.3. Secondary Objectives

- To evaluate the efficacy of the new formulation of rhNGF ophthalmic solution in increasing the number of patients with improved reflex tear production as compared to vehicle at week 8.
- To evaluate the efficacy of the new formulation of rhNGF ophthalmic solution in improving reflex tear production as compared to vehicle at week 8.
- To evaluate the efficacy of the new formulation of rhNGF ophthalmic solution in improving tear film stability as compared to vehicle at weeks 4 and 8.
- To evaluate the efficacy of the new formulation of rhNGF ophthalmic solution in improving ocular surface integrity (corneal and conjunctival epitheliopathy) as compared to vehicle at weeks 4 and 8.
- To evaluate the efficacy of the new formulation of rhNGF ophthalmic solution in improving the severity and frequency of dry eye symptoms as compared to vehicle at weeks 4 and 8.
- To evaluate the efficacy of the new formulation of rhNGF ophthalmic solution in improving dry eye symptoms as compared to vehicle at week 4.
- To evaluate the efficacy of the new formulation of rhNGF ophthalmic solution in improving associated symptoms in DED as compared to vehicle at weeks 4 and 8.
- To evaluate the efficacy of the new formulation of rhNGF ophthalmic solution in improving the quality of life in patients with DED as compared to vehicle at weeks 4 and 8.
- To evaluate the efficacy of the new formulation of rhNGF ophthalmic solution in improving best corrected visual acuity in DED as compared to vehicle at weeks 4 and 8.

2.4. Safety Objectives

- To evaluate safety of the new formulation of rhNGF ophthalmic solution.
- To evaluate tolerability of the new formulation of rhNGF ophthalmic solution.

CCI

- CCI

3. Investigational Plan

[figure not shown]
3.1. Overall Study Design and Plan

This trial is a 4-weeks Phase II, multi-centre, randomized, double-masked, vehicle-controlled, parallel-group, dose-finding clinical trial with 4 Weeks of Follow-Up to evaluate safety and efficacy of a new formulation of recombinant human Nerve Growth Factor (rhNGF) CCI solution at two different concentrations in patients with dry eye disease (DED). It is designed as a superiority clinical trial to assess the efficacy and safety of a new ophthalmic formulation of rhNGF as compared to a vehicle in patients with DED. This is a prospective Phase II trial for a new formulation of CCI (C mcg/mL and C mcg/mL) of rhNGF CCI.

Male or female dry eye disease patients aged ≥ 18 years of any race/ethnicity and eye color will be screened for enrollment to minimize bias in population sampling. All patients successfully enrolled will be randomized at Baseline – Day 1 visit in a 1:1:1 ratio to either of the **CCI** **CCI** of rhNGF formulation (**CCI** mcg/mL or **CCI** mcg/mL) or vehicle.

The study is divided in 3 periods: Screening & Run-in Period (Day -12 \pm 2/Screening Visit 1 to Day 1/Baseline Visit 2); Treatment Period (day 1/Baseline Visit 2, Week 2/Day 13 \pm 1 Visit 3, Week 4/Day 28 \pm 1 Visit 4); Follow-up Period (End of Treatment Visit 4 at Week 4 to End of Follow-up - End of Study Visit 5 at Week 8, Day 56 \pm 2). Procedures for patient inclusion in the study will be performed at both Visit 1 (Screening) and Visit 2 (Baseline). The End of Study Trial visit is expected at Week 8. The maximum total study duration will be about 10 weeks for each patient.

Figure 1: Study Schema

*artificial tears **CCI** provided by the sponsor.

3.2. Study Endpoints

Objectives	Endpoints
Primary Objective 
 To evaluate the efficacy of CCI mcg/mL and CCI mcg/mL concentrations of the new formulation of rhNGF ophthalmic solution versus vehicle, in order to demonstrate superiority of at least one of the concentrations over vehicle in the improvement of ocular symptoms of dry eye in patients with dry eye disease (DED). 	Primary Efficacy Endpoint 
 Mean change from baseline to Week 8 in symptoms of dry eye assessed by SANDE Global Score [Time Frame: week 8 (V5)]

Objectives	Endpoints
Key Secondary Objectives	Key Secondary Efficacy Endpoints

 To evaluate the efficacy of the new formulation of rhNGF ophthalmic solution in increasing the number of patients with improved reflex tear production as compared to vehicle at week 4 	
 Proportion of patients improving to Schirmer-I test without anesthesia ≥ 10 mm/5min in the Study Eye [Time Frame: at week 4 (V4)]

 To evaluate the efficacy of the new formulation of rhNGF ophthalmic solution in improving reflex tear production as compared to vehicle at week 4 	
 Mean change from baseline in Schirmer-I score without anesthesia in the Study Eye [Time frame: at week 4 (V4)]

 To evaluate the efficacy of the new formulation of rhNGF ophthalmic solution in improving ocular surface integrity (corneal epitheliopathy) as compared to vehicle at week 4 	
 Mean change from baseline in total CCI [redacted] in the Study Eye as assessed by the investigator [Time Frame: at week 4 (V4)]
Secondary Objectives	Secondary CCI [redacted] (*) Efficacy Endpoints

 To evaluate the efficacy of the new formulation of rhNGF ophthalmic solution in improving reflex tear production as compared to vehicle at week 8 	
 Mean change from baseline in Schirmer-I score without anesthesia in the Study Eye [Time frame: at week 8 (V5)] Proportion of patients improving to Schirmer-I test without anesthesia ≥ 10 mm/5min in the Study Eye [Time Frame: at week 8 (V5)]

 To evaluate the efficacy of the new formulation of rhNGF ophthalmic solution in improving tear film stability as compared to vehicle at weeks 4 and 8 	
 Mean change from baseline in fluorescein tear break-up time (fTBUT)- in Study Eye [Time Frame: at weeks 4 (V4) and 8 (V5)] CCI [redacted]

 To evaluate the efficacy of the new formulation of rhNGF ophthalmic solution in improving ocular surface integrity (corneal and conjunctival epitheliopathy) as compared to vehicle at weeks 4 and 8 	
 Mean change from baseline in total CCI [redacted] in the Study Eye as assessed by the investigator [Time Frame: at week 8 (V5)] CCI [redacted]

Objectives	Endpoints
	CCI [REDACTED]

 To evaluate the efficacy of the new formulation of rhNGF ophthalmic solution in improving the severity and frequency of dry eye symptoms as compared to vehicle at weeks 4 and 8 	
 Mean change from baseline in symptoms questionnaire (SANDE) scores for severity and frequency [Time Frame: at weeks 4 (V4) and 8 (V5)]

 To evaluate the efficacy of the new formulation of rhNGF ophthalmic solution in improving dry eye symptoms as compared to vehicle at week 4 	
 Mean change from baseline in symptoms of dry eye assessed by SANDE Global Score [Time Frame: at week 4 (V4)]

 To evaluate the efficacy of the new formulation of rhNGF ophthalmic solution in improving associated symptoms in DED as compared to vehicle at weeks 4 and 8 	
 Mean change from baseline of the CCI [REDACTED] [Time Frame: at weeks 4 (V4) and 8 (V5)] CCI [REDACTED]

 To evaluate the efficacy of the new formulation of rhNGF ophthalmic solution in improving the quality of life in patients with DED as compared to vehicle at weeks 4 and 8 	
 Mean change from baseline as assessed by the CCI [REDACTED] QoL scores [Time Frame: at weeks 4 (V4) and 8 (V5)]

 To evaluate the efficacy of the new formulation of rhNGF ophthalmic solution in improving best corrected visual acuity in DED as compared to vehicle at weeks 4 and 8 	
 Mean change from baseline in BCDVA score [Time Frame: at weeks 4 (V4) and 8 (V5)]
Safety Objectives	Safety Endpoints

 To evaluate safety/tolerability of the new formulation of rhNGF ophthalmic solution 	
 Safety will be monitored by the incidence and frequency of treatment-emergent adverse events (TEAEs) assessed throughout the study including run-in period.

 To evaluate safety of the new formulation of rhNGF ophthalmic solution 	
 Mean change from baseline in corneal endothelial cell density in both eyes [Time Frame: at week 8 (V5)] Change from baseline in the proportion of patients with vitritis, retinal or vitreal

Objectives	Endpoints
	
hemorrhages, increase in cup-to-disc ratio, retinal or posterior vitreal detachment, retinal tears, or maculopathy on dilated fundus exam (DFE) in both eyes [Time Frame: at week 8 (V5)]
 
 Mean change from baseline in bulbar conjunctival redness (VBR 10 score) in both eyes [Time Frame: at weeks 4 (V4) and 8 (V5)]

 To evaluate tolerability of the new formulation of rhNGF ophthalmic solution. 	
 Treatment discontinuation rate due to tolerability will also be evaluated.
CCI	CCI

 CCI 	
 CCI
CCI	

(**) Only in patients with CCI
	

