This is the first study with a new formulation of the rhNGF eye drops	rhNGF eye drop formulation at C mcg/mL has been already tested in patients and it is currently marketed (over 16000 patients exposed so far). In this study a new formulation at C mcg/mL and at C mcg/mL will be tested to evaluate safety, efficacy, and tolerability.	In previous studies rhNGF was used at the concentration of C mcg/mL. No difference in safety and possibly a reduction of CCI and CCI is expected with the use of the new formulation, especially considering the CCI in rhNGF concentration. Patients with known allergy to any component of the new formulation will be excluded from participating in the study. AE information and VBR10 data will be collected throughout the study including the Run-In and follow-up period (Visit 2).
Adherence to treatment with vehicle/IMPs/NIMP in the Run-In period, treatment period and Follow-Up period, respectively	During the different phases of the study (Run-In, treatment, Follow-Up), the accountability and the adherence to the specific treatments that will be supplied by the Sponsor should be registered and evaluated	Adherence to the use of the treatments is to be monitored via Patient Diaries implemented for each study period to register the administration of the vehicle (Run-In period), the IMPs/vehicle (treatment period) and preservative free AT (NIMP in Follow-Up period). The Patient Diary will be evaluated to define the adherence to the treatments. A site visit (Visit 3) is programmed after 2 weeks of treatment to check the Patient Diary for medication dosing compliance. The Study Products and AT will be dispensed in controlled amounts at specific visits and used/unused study products will be collected during the successive visits. A check of the returned Study Product vehicle from the Run-In period and IMP or vehicle will be done at every visit starting from visit 2 by independent personnel not directly involved in study activities.
IMP Preparation and storage	New formulation of Study Products to be reconstituted by the Patients (kit containing CCI + diluent) Storage temperature	Instruction for reconstitution will be provided to patients. First vehicle administration during the Run-In period will be performed at the site with the support of clinical staff to show patient reconstitution and administration system. A

Potential Risk of Clinical Significance	Summary of Data/Rationale for Risk	Mitigation Strategy

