10.6.5 Analysis of Safety Variables

Adverse events (AEs) will be coded by System Organ Class (SOC) and Preferred Term (PT), using the Medical Dictionary for Regulatory Activities (MedDRA).

Treatment-emergent AEs (TEAEs) are all events occurring or worsening after the first dose of the IMP. TEAEs will be presented by treatment arm in terms of number of AEs and their incidence by System Organ Class (SOC) and Preferred Terms (PT) using MedDRA. Analyses will be provided also by seriousness, relationship to treatment, severity, and study period

(treatment or follow-up).

Individual AEs will be listed in patient data listings.

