4.3.6. Safety Population (SAF)

The Safety (SAF) population will consist of all patients in the RND population who received at least one dose of the IMP. The Safety population will be analyzed according to the actual treatment received. The SAF population will be used to present results on safety data.

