7.3.1. Exposure and Compliance

The compliance for both the IMP and NIMP will be assessed by number CCI collected in eDiary.

Exposure and compliance to IMP

In treatment period, starting from the first IMP administration done at the baseline visit until the last expected administration, the IMP should be administered CCI (1 drop each time and three times per day). Compliance calculation is based on the number of administrations, CCI.

The duration (days) of exposure to the IMP will be calculated by using data collected in the eCRF as:

$$exposure\ IMP\ (days)_{eCRF} = last\ date\ of\ treatment_{eCRF} - first\ date\ of\ treatment_{eCRF} + 1$$

where first date of treatment and last date of treatment are derived from the dates collected in the eCRF in the Randomization and End of Treatment forms, respectively.

Compliance for the study eye will be derived on the period defined by the exposure (i.e. by using only data collected in the interval defined by first and last date / timepoint collected in the eCRF) as the proportion (%) between the actual number of administrations done in the study eye and the expected number of administrations done in the study eye. CCI

CCI

CCI

CCI

on

CCI

The actual number of administrations done in the study eye is derived by using data collected in the eDiary. CCI

Extra-administrations recorded in the eDiary between first and last administration date (timepoint not recorded in the eDiary) will be also included in the count if administered in the study eye. CCI

The compliance will then be derived as:

$$\text{compliance IMP} = 100 * \frac{\text{number of actual administration}_{e\text{Diary}}}{\text{expected number of administration}_{e\text{CRF}}}$$

Compliance will also be analyzed weekly from baseline to Week 4.

Gross non-compliance will be defined as accountability lower than 80% or greater than 120% and in case of gross non-compliance the patient will be excluded from the Per Protocol dataset.

Exposure and compliance to NIMP (ATs) in the follow-up period.

In follow-up period, the NIMP should be administered CCI each time and CCI per day) from V4 / Week 4 to V5 / Week 8. Compliance calculation is based on the number of administrations. CCI

The duration (days) of exposure to the NIMP will be calculated by using data collected in the eCRF as:

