8.4 Subgroup Analysis

Subgroup analyses of primary and key secondary endpoints will be performed on the following subgroups of baseline characteristics:

- Age class (\leq Median, $>$ Median)
- Race (White, Other)
- Ethnicity (Hispanic or Latino, Not Hispanic or Latino)
- Gender (Male, Female)
- Region (EU, US)
- Certain etiology of dry eye (Yes/No)
- Certain medical history (Yes/No)
- Certain concomitant medications (Yes/No)

CCI

9. Safety Analysis

All safety analyses will be based on the SAF according to the actual treatment received. No formal statistical testing will be performed for safety data.

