9.1. Adverse Events

An Adverse Event (AE) is defined as any untoward medical occurrence in a patient or clinical investigation patient administered a medicinal product and which does not necessarily have a causal relationship with this treatment. An AE can therefore be any unfavorable and unintended sign (including an abnormal laboratory finding), symptom, or disease temporally associated with the use of a medicinal product, whether or not related to the medicinal product.

Treatment-emergent AEs (TEAEs) are defined as AEs that are reported or worsened on or after the first dose of IMP.

Adverse events will be coded according to latest version of MedDRA. Unless otherwise specified, AEs will be summarized by treatment arm and by SOC and PT, with SOC sorted in descending order of patient incidence and PTs within each SOC in descending order of patient incidence in Total group, for each treatment period (“On Treatment period”, “On Follow-up period” and “Overall”). If the total frequency for any 2 or more PTs is equal, the PTs will be presented in alphabetical order.

When summarizing the number and percentage of patients with an event, patients with multiple occurrences of the same AE or a continuing AE will be counted only once. Patients will be presented according to the highest severity (the strongest relationship) in the summaries by severity (of related AEs), if patients reported multiple events under the same SOC and/or PT.

Ocular TEAEs will be summarized separately from non-ocular TEAEs. Ocular TEAEs will be summarized for the Study Eye and the fellow eye. Non-ocular TEAEs will be summarized regardless of the Study Eye or the fellow eye.

By-patient listings of ocular and non-ocular AEs will be presented by treatment and ordered by site.

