13.2. Missing Date Imputation for Missing or Partial Dates

Table 3: Algorithm for Treatment Emergence of Adverse Events.			
AE start date	AE end date	RULE for TEAE definition	RULE for definition of study period for TEAEs only: “On Treatment” / “On follow-up”
Known	Known, Partial or Missing	If start date < IMP start date, then not TEAE If start date ≥ IMP start date, then TEAE	If start date > date of last IMP administration, then “On Follow-up”. Otherwise, “On Treatment”
Partial, but known components show that it cannot be on or after IMP start date	Known, Partial or Missing	Not TEAE	Not applicable
Partial, could be on or after IMP start date OR Missing	Known	If stop date < IMP start date, then not TEAE If stop date ≥ IMP start date, then TEAE	If TEAE, then “On Treatment”
	Partial	Impute stop date as latest possible date (i.e. last day of month if only day is missing, Dec if only month is missing, 31 st Dec if day and month are both missing, then: If stop date < IMP start date, then not TEAE If stop date ≥ IMP start date, then TEAE	
	Missing	Assumed TEAE	

Table 4: Algorithm for Prior / Concomitant medications.		
MEDICATION start date	MEDICATION end date	RULE for Prior / Concomitant definition
Known	Known	If stop date < IMP start date, then “prior” If stop date ≥ IMP start date, then “concomitant”
	Partial	Impute stop date as latest possible date (i.e. last day of month if only day is missing, Dec if only month is missing, 31 st Dec if day and month are both missing, then: If stop date < IMP start date, then “prior” If stop date ≥ IMP start date, then “concomitant”
	Missing	Assign as concomitant
Partial OR Missing	Known	If stop date < IMP start date, then “prior” If stop date ≥ IMP start date, then “concomitant”
	Partial	Impute stop date as latest possible date (i.e. last day of month if only day is missing, Dec if only month is missing, 31 st Dec if day and month are both missing, then: If stop date < IMP start date, then “prior” If stop date ≥ IMP start date, then “concomitant”
	Missing	Assign as concomitant

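### The first-listed safety endpoint counts TEAEs over the run-in, but the SAP's TEAE definition and safety population leave run-in adverse events without a planned summary table

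*SAP*

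**What the plan says.** **Endpoint.** SAP Section 3.2 and Protocol Sections 1.1 and 3.1 place first among the safety endpoints the incidence and frequency of TEAEs, "assessed throughout the study including run-in period".

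**Definition.** SAP 9.1: "Treatment-emergent AEs (TEAEs) are defined as AEs that are reported or worsened on or after the first dose of IMP". Protocol 10.6.5 agrees: "Treatment-emergent AEs (TEAEs) are all events occurring or worsening after the first dose of the IMP". The date algorithm in SAP Appendix 13.2 (Table 3) puts it as a rule: "If start date < IMP start date, then not TEAE".

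**When IMP starts.** SAP 7.3.1 describes the treatment period as "starting from the first IMP administration done at the baseline visit until the last expected administration" and takes the first treatment date from the Randomization form. SAP 7.3 names the run-in vehicle separately from IMP.

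**Periods.** AE summaries in SAP 9.1 are given for On Treatment, On Follow-up and Overall. Table 3 assigns a period to TEAEs only. Neither provides for the run-in.

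**Population.** SAP Section 9: "All safety analyses will be based on the SAF according to the actual treatment received". The SAF is "all patients in the RND population who received at least one dose of the IMP" (SAP 4.3.6).

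**Collection and listing.** AEs are recorded from consent (Protocol 9.3), and an eCRF is completed for every consented patient, screen failures included (SAP 4.3.1). SAP Section 4 lists all eCRF data, SAP 9.1.1 lists all AEs by patient, and SAP 9.1.5 lists all SAEs.

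**The concern.** The endpoint asks for incidence and frequency over a span that includes the run-in. Under the definition, an event that starts and ends in the run-in is not treatment-emergent, so it cannot count towards an endpoint made of TEAEs. The analyst must either ignore the run-in clause or depart from the definition, and the SAP does not say which. SAP Section 11, which records changes to the planned analysis, is silent on it.

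This matters because the study is the first with the new formulation, and Protocol 2.3.2 describes the vehicle as carrying the new excipient. Every eligible patient uses that vehicle for 12 ± 2 days before randomisation (Protocol 2.2). Run-in adverse events are the only experience of it in patients who take it but are not randomised, and there is no data monitoring committee (Protocol 11.2). What is at stake is a complete descriptive account of vehicle tolerability, not a between-arm comparison.

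**Working it through.** **1. Can a run-in event be a TEAE?** Take an event with known dates that starts on Day -8 and resolves on Day -5.

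| Rule | Source | Result |
|---|---|---|
| Endpoint covers the run-in | SAP 3.2 | Should be counted |
| TEAE starts at first IMP dose | SAP 9.1; Protocol 10.6.5 | Not a TEAE |
| First IMP dose is at baseline | SAP 7.3.1 | Event precedes it |
| Start date before IMP start | SAP 13.2, Table 3 | Not a TEAE |
| Period allocation | SAP 9.1; Table 3 | None available |
| Overall TEAE summary | SAP 9.1.1 | Excluded |
| By-patient listing of all AEs | SAP 9.1.1 | Included, if the patient is in the SAF |

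The endpoint row conflicts with every rule that produces a summary table.

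**2. Which run-in events can still reach a table?** There are three narrow routes.

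- An event that worsens after IMP starts is a TEAE by the SAP 9.1 text, although the start-date rule in Table 3 does not reflect worsening.
- An event with a missing start date, or a partial one that could fall on or after IMP start, becomes a TEAE if its stop date is on or after IMP start, or if the stop date is missing.
- The table of AEs of special interest (SAP 9.1.6) is not expressly limited to TEAEs.

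**3. Exposure without an incidence summary.** Inputs are 291 randomised (SAP 4.1) and 12 ± 2 days of run-in (Protocol 2.2).

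- Central: 291 × 12 = 3,492 patient-days.
- Range: 291 × 10 = 2,910 to 291 × 14 = 4,074 patient-days.

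**4. Patients outside the SAF.** The plan's own figure comes first: 291 × 1.20 = 349.2, which reproduces the stated 350 or so to be screened.

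- Not randomised: 350 − 291 = 59 (59/350 = 17%).
- If 20% were instead a share of those screened: 291/0.80 = 363.75, so 364, and 364 − 291 = 73.

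Eligibility is checked at Visit 1, before any vehicle, and again at Visit 2, after the run-in. The documents do not split failures between the two visits. The number exposed but not randomised therefore lies between 0 and 59 on the plan's figure, or between 0 and 73 on the alternative reading. The upper bound assumes that nobody fails at Visit 1.

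**The case against.** **The data are not lost.** This stands. AEs are collected from consent and listed, so a reader who infers that the plan discards run-in events goes too far. But a listing does not give the incidence and frequency that the endpoint promises. For exposed patients who were never randomised the listing route is only arguable: SAP Section 4 and 9.1 arrange listings by treatment, which these patients lack, and Section 9 confines safety analyses to the SAF.

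**Run-in vehicle is IMP.** Protocol 8.1 does call the run-in drops IMP (vehicle), so the Protocol's first IMP dose could be read as Visit 1. The SAP dates IMP from baseline and governs planned analyses where the documents differ (SAP Section 1). Even on the Visit 1 reading the SAF would require randomisation, and Table 3 would class run-in events as On Treatment in an arm not yet assigned.

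**The Overall period covers the run-in.** SAP 9.1 speaks of AEs when it introduces the periods, but the overall summary in 9.1.1 is one of TEAEs, and no period is defined for events before IMP.

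**Vehicle safety is tabulated anyway.** This stands in part. About 97 patients receive the same vehicle for four weeks in the randomised arm, and their TEAEs are summarised. Run-in events carry no between-arm information, and no safety testing is planned. The randomised vehicle arm does not, however, include patients who left before randomisation.

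**The risk table is satisfied.** This stands. Table 2 in Protocol 2.7 relies on collecting run-in AE data as mitigation, and collection does happen. A reader might infer that the mitigation fails; the documents do not support that.

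**Rewording the endpoint would be enough.** It would remove the contradiction, but run-in events would still have no summary.

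**Conclusion.** The conflict is real and lies in the current text of both documents. The first-listed safety endpoint cannot be produced under the SAP's own TEAE definition, periods and population. For randomised patients the gap is a missing summary table covering about 3,492 patient-days of vehicle use (2,910 to 4,074). This is a count of exposure, not an estimate of missed events. For exposed patients who were not randomised, the gap is exclusion from the SAF with uncertain listing; their number is 0 to about 59, and zero is possible.

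Three stronger conclusions might be inferred and are not supported. The documents do not rank the safety endpoints, so this one is first-listed rather than main. They give no basis for saying that those who leave in the run-in are the patients least tolerant of vehicle, since a Visit 2 failure may simply no longer meet the symptom or sign thresholds. And no comparative safety or efficacy conclusion depends on the point.

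The conclusion assumes that the SAP's dating of first IMP to baseline is intended and that no unredacted output elsewhere covers the run-in. It should be corrected: the remedy is cheap and concerns a stated endpoint.

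**What to change.** - Reword the endpoint in SAP 3.2, and in the Protocol at its next revision, as TEAEs, plus AEs with onset during run-in.
- Define a run-in exposed set: all patients who took at least one run-in vehicle drop, randomised or not.
- Add one descriptive table, by SOC and PT, of AEs with onset from the first run-in drop to before the first IMP dose in that set. Present it as a single column, because no arm has been assigned.
- Add a listing of the same events that expressly includes patients not randomised.
- Reconcile the Protocol's IMP (vehicle) label for run-in drops with the SAP's IMP start date, so that first IMP dose has one meaning.

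The cost is some SAP wording, one analysis flag and one or two extra outputs from data already collected. The table will be uncontrolled and should be read as such.
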